1.0 Objectives

1.1 Study Objectives

The current proposal aims to establish proof-of-concept that neural cue-reactivity can serve as an early, objective marker of electronic cigarette (ECIG) addictive potential. Further, this proposal will examine the effect of flavor and nicotine concentration on the addictive potential of ECIGs to aid research informing U.S. Food and Drug Administration (FDA) flavor regulations and smoking cessation.

The specific aims of the study are:

Aim 1: Determine if smokers and e-cigarette users have pre-conditioned neural cue-reactivity to tobacco or fruit-flavored ECIG odors.

Aim 2: Examine the effect of flavor and nicotine on ECIG odor cue-reactivity after conditioning.

Aim 3: Determine if strawberry vanilla flavor results in stronger cue-reactivity than tobacco flavor.

Hypothesis: We expect the group assigned to the 18 mg/ml strawberry vanilla flavor to show larger increases in neural cue-reactivity to their assigned odor than the 18 mg/ml tobacco flavor group.

1.2 Primary Study Endpoints

The primary study endpoint is odor cue-reactivity. Functional magnetic resonance imaging (fMRI) will be used to measure neural cue-reactivity to the ECIG odors presented in the study.

1.3 Secondary Study Endpoints

The secondary study endpoints are cigarette dependence, ECIG dependence, ECIG liking and satisfaction, and flavor liking.

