7.4.3 Method for Assigning Subject to Treatment Groups

Blocked randomization stratified across gender and matched for age will be accomplished with a 1:1:1:1 ratio of condition assignments with a goal of 56 randomized over a 7 month recruitment period. The randomization list will be stored in a password protected document that will only be accessed by unblinded study personnel.

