8.3 Statistical methods

Images collected during the fMRI odor cue reactivity task will be preprocessed using a standard Functional Magnetic Resonance Imaging of the Brain Software Library (FSL) software pipeline. Blood oxygen level dependent (BOLD) activation during the tobacco, strawberry vanilla, and rose flavors will be modeled using a double-gamma hemodynamic response function, contrasted to one another, and merged across the two runs for each participant. To create images that capture changes from baseline to post-conditioning, a difference z- statistic image will be calculated by subtracting the baseline image from the post-conditioning image. The lavender odor is an experimental control condition that encourages participants to maintain attention and task engagement during the MRI scan. It is not part of the endpoints of the study.

Aim 1: Determine if smokers and ECIG users have pre-conditioned neural cue-reactivity to tobacco or strawberry-vanilla ECIG odors. One- sample t-test will be conducted on the contrast of tobacco > strawberry vanilla, tobacco > rose, strawberry vanilla > rose to identify anatomical brain regions where tobacco elicits greater neural activation over strawberry vanilla and rose odors and strawberry vanilla elicits greater activation over rose odors. We expect tobacco odor to elicit greater activation in the ventral striatum, amygdala, anterior insula, and OFC than the strawberry vanilla and rose for combustible cigarette smokers and tobacco-flavored e-cigarette users. We expect strawberry-vanilla odor to elicit greater activation in ventral striatum, amygdala, anterior insula, and OFC than tobacco and rose for fruit-flavored e-cigarette users.

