Aim 2: Examine the effect of flavor and nicotine on ECIG odor cue-reactivity after conditioning. Two-sample t-test will be conducted in FSL for the strawberry vanilla>rose and tobacco>rose odor difference score z- statistic images comparing the 18 mg to 0mg nicotine content ECIG groups. A paired two-sample t-test will be conducted to compare the tobacco>rose and strawberry vanilla>rose odor difference score z-statistic image separately for each 18 mg/ml ECIG flavor group. These t-tests will identify anatomical regions with significant effects of nicotine level and assigned vs. unassigned flavor over time. We expect that BOLD activity in regions implicated in smoking cue-reactivity will increase more over the conditioning phase for the 18 mg nicotine group compared to the 0mg nicotine group and for odors from the assigned vs. unassigned flavor.

Aim 3: Determine if strawberry vanilla results in stronger cue-reactivity than tobacco flavor. A two-sample t-test will be conducted for the assigned flavor (strawberry vanilla or tobacco) > control rose difference score z- statistic images comparing the flavor groups. These t-tests will identify anatomical regions with significant flavor group (tobacco vs. strawberry vanilla) by time (baseline to post-randomization) interaction effects on each odor image. For this analysis, only the 18 mg/ml nicotine content flavor groups will be included.

Exploratory Behavioral Aim: Determine if changes in flavor cue-reactivity are associated with changes in ECIG satisfaction, liking, craving, and dependence. One-sample t-tests will assess for anatomical regions where BOLD changes in odor cue-reactivity are correlated with changes in behavioral measures of e- cig satisfaction, craving, and dependence collected at the 2-week check-in and post-randomization visit, and changes in ECIG liking collected at the baseline and post-randomization visits.

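### None of the four secondary endpoints has a planned comparison by randomized flavor or nicotine group, although the data collected would allow one

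*Combined protocol and SAP*

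**What the plan says.** Section 1.3 lists the endpoints: "The secondary study endpoints are cigarette dependence, ECIG dependence, ECIG liking and satisfaction, and flavor liking". Section 1.1 gives, as the second of two stated purposes, that "this proposal will examine the effect of flavor and nicotine concentration on the addictive potential of ECIGs". Section 7.4.3 allocates four arms (two flavors by two nicotine levels) at a "1:1:1:1 ratio of condition assignments with a goal of 56 randomized".

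Section 8.3 then sets out these analyses:
- **Aim 1:** a one-sample "t-test will be conducted on the contrast of tobacco > strawberry vanilla, tobacco > rose, strawberry vanilla > rose", on baseline images.
- **Aim 2:** a two-sample test on difference-score "statistic images comparing the 18 mg to 0mg nicotine content ECIG groups", plus a paired comparison of the two odors within each 18 mg/ml flavor group.
- **Aim 3:** "A two-sample t-test will be conducted for the assigned flavor (strawberry vanilla or tobacco) > control rose difference score" images, in the 18 mg/ml arms only.
- **Exploratory Behavioral Aim:** "One-sample t-tests will assess for anatomical regions where BOLD changes in odor cue-reactivity are correlated with changes in behavioral measures", namely ECIG satisfaction, craving and dependence (from Visits 3 and 4) and ECIG liking (from baseline and Visit 4).

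Section 9.7, under safety monitoring, adds a paired test of change from baseline in cigarettes per day, CO and unspecified subjective measures. Section 8.2 gives power for cue-reactivity only.

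**The concern.** An endpoint named in section 1.3 should have an analysis that answers a question the trial was built to ask. The design is a randomized two-by-two layout, and dependence, liking and satisfaction are its behavioral measures of how flavor and nicotine affect appeal and addiction. Randomization protects a between-arm estimate of each factor, but the plan never asks for one on these endpoints.

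Neither planned analysis substitutes for it. A BOLD-behavior correlation says whether brain and behavior move together, not whether 18 mg/ml or strawberry vanilla changed the behavior. A change from baseline with no comparison group mixes any product effect with the passage of time and with replacing cigarettes, which section 7.2.3 tells participants to do. If arms are compared later without a written model, the choice of arms, visit and adjustment can be made after the results are seen.

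**Working it through.** **1. Endpoint by endpoint**

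| Secondary endpoint | Collected (Table 1; 7.2.10) | Use in 8.3 | Use in 9.7 | Compared by arm |
|---|---|---|---|---|
| Cigarette dependence | Visits 2, 3, 4 | Not named | Possibly, as a subjective measure | No |
| ECIG dependence | Visits 3, 4 | Correlate of BOLD change | Not computable: no Visit 2 value | No |
| ECIG liking and satisfaction (ECIG evaluation scale) | Visits 3, 4 | Correlate of BOLD change | Not computable: no Visit 2 value | No |
| Flavor liking (in-scanner rating) | Both scans (Visits 2, 4) | Not named, unless baseline ECIG liking means this rating | Possibly, as a subjective measure | No |

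Endpoints with a comparison by flavor or nicotine: 0 of 4. Every between-group test in 8.3 has an image as its outcome. I take the scale in row three to be the ECIG evaluation scale, since no other ECIG liking or satisfaction scale appears in Table 1. That the correlation analysis pools the arms is an inference from its one-sample form; the section names no group factor.

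**2. The plan's own between-group figure**

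Section 8.2 states 60% power for cue-reactivity change between nicotine and flavor groups. Taking a medium effect as d = 0.5 (no number is given), 28 v 28, and two-sided 0.10 carried over from the preceding clause:

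power = Φ(d × √(n/2) − 1.645) = Φ(0.5 × √14 − 1.645) = Φ(0.226) = 0.589

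The exact noncentral t value is 0.580. The figure reproduces, and it matches a factor-level comparison of 28 v 28. No equivalent is stated for any secondary endpoint.

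**3. Precision if the comparison were added**

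The 95% half-width, in SD units, is t(0.975, 2n − 2) × √(2/n):
- 28 v 28 (56/2, everyone analyzed): 2.005 × 0.267 = 0.54
- 22 v 22 (assumed loss before Visit 4): 2.018 × 0.302 = 0.61
- 14 v 14 (a single pair of arms): 2.056 × 0.378 = 0.78

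Adjusting for a Visit 2 value multiplies this by √(1 − r²). With an assumed r of 0.5 to 0.7 and 28 v 28, the half-width is 0.46 to 0.38. That gain is open only to cigarette dependence and flavor liking; ECIG dependence and the ECIG evaluation scale have no Visit 2 value. At d = 0.5, 28 v 28 gives power of 0.45 at two-sided 0.05; 80% power needs d = 0.76.

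**4. A trap in scoring flavor liking**

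An assigned-minus-unassigned rating looks natural but changes sign with the flavor arm. Suppose everyone prefers strawberry vanilla by d SD of the preference score at both visits and nothing changes. The mean score is +d in the strawberry vanilla arms and −d in the tobacco arms, a difference of 2d at each visit. Adjusting for Visit 2 with slope r removes only r × 2d, leaving a false flavor effect of 2d(1 − r). With an assumed d = 0.5, that is 2 × 0.5 × 0.5 = 0.50 SD at r = 0.5 and 2 × 0.5 × 0.3 = 0.30 SD at r = 0.7. A strawberry-vanilla-minus-tobacco score, with the same sign in all arms, has equal expected baselines and leaves no such bias.

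**The case against.** The best defense is that this is an imaging proof-of-concept. The first purpose in section 1.1, repeated in 2.3, is to establish neural cue-reactivity as a marker. No aim or hypothesis concerns an arm effect on dependence, liking or satisfaction. For a marker study, a BOLD-behavior correlation is a relevant analysis. Section 8.2 also says that between-subject analyses look for trends rather than significance, and power for a medium effect would be only 0.45 at two-sided 0.05.

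Most of this stands, and it limits the point. A reader might infer that the trial leaves its flavor and nicotine question unanswered. The documents do not support that: Aims 2 and 3 compare the primary imaging endpoint by randomized nicotine and flavor group. A reader might also infer that the trial cannot show a behavioral effect at all. That too goes beyond the documents: the measures are collected in all four arms and nothing excludes a comparison. What is missing is the planned analysis.

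The objection does not remove the gap. The protocol itself chose these four as secondary endpoints, and low power is a reason to report estimates with intervals, not to omit the contrast. The rank-sum test offered in 9.7 is a two-sample method, but no groups are named and it stands as the alternative to a paired test, so it supplies no arm comparison.

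**Conclusion.** The point holds for the secondary endpoints only. As planned, none of the four yields a randomized estimate of a flavor or nicotine effect, and for ECIG dependence and the ECIG evaluation scale even the change from baseline in 9.7 is unavailable.

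An added factorial comparison would have an unadjusted half-width of 0.54 SD at best, and 0.61 SD with an assumed 22 per group. The best case needs all 56 at Visit 4, whereas section 3.3.2 replaces only withdrawals before randomization. Cigarette dependence will be less precise again, because section 3.1 admits daily e-cigarette users as an alternative to smokers and the documents do not give the mix. These would be supportive estimates able to rule out large effects, not confirmatory tests. The change is worth making because it is cheap; it does not affect the primary analysis.

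**What to change.** Add to section 8.3 one linear model per secondary endpoint at Visit 4:
- **Factors:** nicotine (18 v 0 mg/ml) and flavor, using all four arms.
- **Adjustment:** gender (the randomization stratum), age (matched on in 7.4.3) and user type (smoker or e-cigarette user). Add the Visit 2 value only where it was collected before the device was dispensed; section 7.2.3 allows some Visit 2 assessments up to 3 days after the scan visit. Where no Visit 2 value exists, compare Visit 4 values; randomization makes this valid.
- **Cigarette dependence:** analyze participants who smoke at baseline.
- **Flavor liking:** use the strawberry vanilla minus tobacco odor rating, scored the same way in all arms and adjusted for the same score at Visit 2. Do not use assigned minus unassigned. The flavor coefficient is then the effect of assignment on relative liking, and the nicotine-by-flavor term shows whether nicotine changes it.
- **Reporting:** main effects with 95% confidence intervals, labelled supportive. The interaction is exploratory for the other three endpoints.

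State also whether baseline ECIG liking in 8.3 means the in-scanner rating. The cost is a paragraph and a few extra regressions on data already scheduled, with no change to trial conduct.

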2.0 Background

2.1 Scientific Background and Gaps

There is growing evidence that ECIGs can help smokers reduce the number of cigarettes they smoke per day or quit completely.¹⁻⁴ Regular ECIG users report that the variety of flavors, like fruit and dessert flavors, help to curb cigarette cravings and maintain abstinence.⁵⁻⁶ These reports are supported by population data showing that smokers who use flavored ECIGs smoke fewer cigarettes than those who use unflavored or tobacco-flavored ECIGs.⁷ Along with the potential for flavors to help smokers switch to ECIGs, appealing flavors have also been identified as a primary contributor to the initiation of ECIG use among youth, which could result in a new generation of nicotine users. The FDA is calling for more information on how flavors affect the addictive potential of ECIGs to determine if flavor is a necessary feature for satisfying adult smokers. However, there remains a critical need for new, innovative methods of measuring the addictive potential of tobacco products that can predict use behaviors.⁸

Compulsive drug-seeking behavior is known to be driven by neuroadaptations in the brain that can serve as early markers of addiction development.⁹ A neurobehavioral process that occurs across substances of abuse is the development of conditioned reactivity to drug cues.¹⁰ Drug cues alone can elicit craving, drug-seeking behavior, and relapse.¹⁰⁻¹¹ Cue-reactivity is mediated by neuroadaptations in mesocorticolimbic circuitry that occur when environmental and sensory stimuli become associated with the dopaminergic effects of the drug.¹²⁻¹⁴ Physiological cue-reactivity has been found to develop after only 11 pairings between environmental cues and smoking.¹⁵ Using functional magnetic resonance imaging (fMRI), our group was the first to show evidence of neural reactivity to visual ECIG images among regular ECIG users.⁶ Given that food-related flavors independently elicit reactivity throughout reward and learning brain circuitry that drives conditioning, fruit and dessert ECIG flavors have the potential to significantly enhance ECIG cue conditioning.¹⁶⁻¹⁷

2.2 Previous Data

[name] and The Penn State Tobacco Center of Regulatory Science (TCORS) team conducted a survey of over 6,000 ECIG users and found that nicotine and flavor play primary roles for former smokers who quit using e- cigs.⁵ Most participants used e-liquids with nicotine concentrations between 13 and 18 mg/ml and dependence increased with the level of nicotine concentration.¹⁸ Many participants reported that they switched from cig-a-like devices to advanced devices that deliver more nicotine and offer a variety of flavor options.¹⁹ ECIG users' top-rated flavors fell into 3 categories; tobacco, dessert/sweets, and fruit.⁵

In preliminary fMRI research on the neural effects of ECIG use, we found that ECIG images elicited stronger neural activation throughout the cingulate, temporal, and occipital cortices than the control images of electric toothbrushes and cortical activation to ECIG cues increased after ECIG use.^{20 21} Reductions in withdrawal symptoms after ECIG use were associated with changes in resting state functional connectivity in brain networks involved in emotion, cognitive control, visuospatial awareness, and salience, and between reward and executive control networks.²⁰ Surprisingly, neural connectivity changes were not influenced by the amount of nicotine delivered during ECIG use, which varied widely with participants' personal devices.^{20 21} This finding supports our hypothesis that other conditioned features of ECIG use influence neuroadaptations.

The Penn State Center for Nuclear Magnetic Resonance Research (CNMRR) has pioneered the study of human olfaction. [name] and his colleagues have shown that the neural olfaction sensory system overlaps with limbic and prefrontal regions involved in associative learning, including the hippocampus, orbitofrontal cortex (OFC), and anterior cingulate cortex (ACC).^{22 23} They have linked odor to multisensory associative learning that occurs within the olfactory cortex.¹⁷ They were the first to apply their work in olfaction to smoking and found that the smell of fresh tobacco enhances smoking cue reactivity and the perceived enjoyment and reward of smoking.^{24 25} Using fMRI, they found that neural cue-reactivity to smoking odors is associated with self-reported control over craving, supporting the role of odor in smoking behavior.²⁵ This project proposes to use the olfactometer (Emerging Tech Trans inc), a commercially available MRI device developed by researchers at the CNMRR.

2.3 Study Rationale

The proposed study will establish proof-of-concept for using innovative olfaction fMRI cue-reactivity to measure how product characteristics, such as flavor and nicotine, affect the addictive potential of ECIGs. This method can inform FDA regulations on the abuse liability of new flavored tobacco products and provide an early biomarker of success for smokers attempting to switch from cigarettes to ECIGs.

3.0 Inclusion and Exclusion Criteria

3.1 Inclusion Criteria

1. Aged 21-60
2. Smoke filtered cigarettes/machine-rolled cigarettes (≥ 5 cigarettes per day) or daily e-cigarette use for past year
3. No serious quit attempt in prior month. This includes use of any FDA approved smoking cessation medication (varenicline, bupropion [used specifically as a quitting aid], patch, gum, lozenge, inhaler, and nasal spray) in the past 1 month as an indication of treatment seeking.
4. Willing to supplement cigarette smoking with ECIG use for 4 weeks or replace e-cigarette with study product for 4 weeks
5. Willing to attend regular visits over a 4-week period (not planning to move, not planning extended vacation, no planned surgeries)

6. Willing to undergo two fMRI scans
7. Able to read and write in English
8. Able to understand and consent to study procedures
9. Access to computer with internet service that allows for use of Zoom

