3.3 Early Withdrawal of Subjects

3.3.1 Criteria for removal from study

The Principal Investigator reserves the right to remove a participant from the study for any reason, based on their discretion.

Early Withdrawal Criteria Prior to Randomization: Participants who met any criteria below at Visit 2 will be considered for withdrawal prior to randomization:

1. Starting nicotine replacement therapy (e.g., patch, gum, lozenge, inhaler, nasal spray, Zyban, Chantix)
2. Use of other non-cigarette tobacco products in the past 7 days
3. Reporting a quit attempt in the past 7 days
4. Participant is not able to attend their Visit 2 Randomization visit within the study window.

General Withdrawal Criteria

1. Missing their study visit window: If a participant misses their study visit window, the participant will be considered for withdrawal from the study.
2. Not maintaining ECIG and cigarette use diary
3. New pregnancy: Participants who report a new pregnancy at any point during the study will be withdrawn.
4. Suicide attempt: If at any time during the study it is discovered that a participant has made a suicide attempt, they will be withdrawn from the study.
5. Cardiovascular disease (CVD) event requiring inpatient hospitalization: CVD typically includes MI (heart attack), PTCA (angioplasty/stenting), bypass surgery, stroke, peripheral vascular disease (arterial blockages in arms or legs leading to procedure or surgery). Less common CVD problems would be new cardiac arrhythmias (e.g., new atrial fibrillation) or new valvular disease (e.g., mitral or aortic regurgitation).
6. DVT/PE (deep vein thrombosis/pulmonary embolism, i.e., blood clots in the venous system) requiring inpatient hospitalization.
7. Psychiatric Inpatient Hospitalization: A participant will be withdrawn if he/she reports an inpatient hospitalization for psychiatric reasons at any time during participation in the study.
8. Participant choice: Participants may choose to remove themselves from the study by informing the research team in writing, by phone call or in person at any point during the study. If they choose to remove themselves from the study, they will not receive any further contact from the study center.
9. Adverse events related to ECIG use: Adverse events will be monitored at every study visit.
10. Worsening substance abuse in which the participant is behaving inappropriately at visits or demonstrates an inability to continue with the study.

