7.2.3 Randomization/Pre-Conditioning fMRI Visit (Day 0) – In Person/Remote

Participants will sign their long form written consent at this visit prior to any further study procedures.

Exhaled breath CO (eCO) will be measured at the start of the visit. A urine sample will also be collected and tested for cotinine using the NICCheck cotinine test and pregnancy if participants are of child bearing potential. Eligible participants will then be randomized to one of the four conditions and asked to complete the baseline assessments. This includes the standardized smell test (B-Sit), adverse events assessment and computerized questionnaires of cigarette use, cigarette dependence, liking, and withdrawal as indicated in Table 1. Some of the measures can be done remotely via Zoom, others will need to be completed in person. The remote assessments will be conducted via a Zoom session within 3 days following the scheduled in-Person MRI. The remote visit will only occur after written consent has been obtained. This is being done to limit the amount of face-to-face time during study visits.

Then, participants will complete the fMRI odor cue-reactivity task in the MRI scanner lasting approximately 45 minutes. During the scan, participants will be administered four flavors in separate 4 minutes blocks for eight runs. The flavors will be delivered to the participant's nostrils via tubing from the olfactometer machine. The release of the flavors will be timed with participants' natural rate of respiration and randomized across blocks. At the end of this visit participants will be given the ECIG device and 4-week supply of their randomly assigned flavor cartridges (approximately 2 cartridges/day) and instructed on how to use the device.

Participants will be instructed to take at least 50 puffs per day from the ECIG device to replace conventional cigarette smoking. The participant will be instructed to bring back all used and unused cartomizers to the study center. ECIG puffs per day and cigarettes per day will be recorded on a daily log. Participants will receive a daily REDCap survey link via text message using the Twilio service. Participants will be instructed on how to complete the survey and will be provided with a paper log to tally their cigarette use throughout the day. Participants who are unable or unwilling to receive study text messages will track their cigarette use on the paper log only.

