7.2.4 Conditioning Phase Check-in Visit (Day 14 ± 7 days) - Remote

Participants will take part in a remote visit via Zoom to report their ECIG use and cigarettes per day (CPD) (collected in the daily logs). Participants will complete the measures outlined in Table 1. Participants will complete an adverse events assessment and discuss challenges to using their e-cig daily and study staff will assist in problem solving barriers to compliance. At the end of the visit participants will be instructed to remain abstinent from all tobacco products including their ECIG for 14 hours prior to the next study visit and to eat before their next study visit.

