7.2.5 Post-Conditioning fMRI Visit (Day 28 ± 7 days) – In Person/Remote

Participants will attend a final visit to complete biomeasures, computerized surveys, the adverse events assessment, and the same fMRI tasks as the baseline MRI visit as indicated in Table 1. Some of the measures can be done remotely via Zoom, others will need to be completed in person. The remote assessments will be conducted via a Zoom session ± 3 days of the scheduled in-Person MRI. This is being done to limit the amount of face-to-face time during study visits. eCO will be measured and urine will be collected for cotinine and pregnancy tests. At the end of the visit, participants will be debriefed and counseled on smoking cessation. All participants will be given a copy of the Surgeon General's booklet 'How Tobacco Smoke Causes Disease' (SEE ATTACHMENT: Surgeon General's Booklet).

Table 1: Measures Table (Black X – In Person; Green X – Remote)

	Final Screening	Randomization/ Pre-Conditioning fMRI	Check-In	Post- Randomization fMRI
Visit	1	2	3	4
Day	-7	0	14	28
QUESTIONNAIRES				
Visit Screener	X			
Tobacco Use History	X			
Name Registry	X			
MRI Safety Form	X	X		X
Demographics	X			
Medical History	X			
Concomitant Medications	X	X	X	X
Adverse Event Assessment		X	X	X
Cigarette Details	X			
CCQ (Clinical COPD Questionnaire)	X	X	X	x
Alcohol Audit-C	X			
NIDA Quick Screen	X			
Environmental Smoke Questionnaire	X			
MINI Psychiatric Interview	X			
Daily Smoking and ECIG Use Logs	X (cigarette only)	X	X	X
Cigarette Dependence (Fagerstrom and Penn State Cigarette Dependence Index)		X	X	X
Minnesota Withdrawal Scale		X	X	X
Craving		X	X	X
Cigarette liking scale		X	X	X
ECIG Use History	X	X	X	X
ECIG evaluation scale			X	X
ECIG Side Effects			X	X
ECIG dependence			X	X
ECIG Perceived Health Risk			X	X
ECIP Patterns of Use			X	X
Perceived Benefits and Harms of Using ECIG		X		X
PROCEDURES				
B-SIT Smell Test		X		
fMRI Cue-Reactivity Task in Scanner		X		X
BIOMEASURES				
Pregnancy Test		X		X
Exhaled CO		X		X
Urine Sample Collection		X		X
NICCHECK Rapid Cotinine Test		X		X

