7.4 Test Article(s) (Study Drug(s) and/or Study Device(s))

7.4.1 Description

The ECIG used will be the EGO ECIG. Previous work has shown that the EGO ECIG was capable of delivering nicotine to its users.²⁶ This ECIG is made up of 2 parts, a battery and a cartomizer. The cartomizer contains the heating element and the liquid. The liquid used in the cartomizer will contain either 0 mg/ml or 18 mg/ml of nicotine and be either tobacco or strawberry vanilla

flavor. The nicotine concentration in the liquid and the flavor will be determined by random assignment. The cartomizers will be filled with liquid by the researchers and will be used once by the participant and returned to researchers.

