10.0 Risks

10.1 ECIG use:

- There may be some unknown risks related to the use of ECIGs though these risks are not considered to be greater than risks associated with conventional cigarette use.
- The most common side effects associated with using an ECIG are changes in taste, dehydration, mucus in throat/sinus, dry mouth, dry cough, throat irritation, mouth irritation, sore throat, mouth ulcers, dizziness, headache, and nausea.
- There are reports that some people who use e-cigarettes have experienced seizures, with most involving youth or young adult users. Participants with a history of seizures or take medications to prevent seizures will be excluded from the study.
- There have been some reports of serious lung illnesses among those who used e-cigarettes, and even some cases of death as a result (not all causes of death have been identified). The investigations being conducted by the Centers for Disease Control and Prevention (CDC) and the Food and Drug Administration (FDA) have found that the majority of people experiencing these

illnesses were using e-cigarette products that contained tetrahydrocannabinol (THC) and/or products that were bought off the street or from other illicit channels and so it is important that participants avoid such products. The e-cigarette products used in this study do not contain THC and were bought from manufacturers where quality testing and control is performed. Nonetheless, participants will be advised to call their doctor immediately if they experience cough, shortness of breath, chest pain, nausea, vomiting, diarrhea, or fever after using their e-cigarette. Participants will be told to only use the e-cigarette and liquid pods (cartridges) given to them by the researchers and to not tamper with their e-cigarette or use other liquids with the e-cigarette device.

- If stored improperly (in pocket or where the ECIG device can turn on accidentally), overheating of the device may occur, which presents a minor burn risk.
- Electronic cigarette liquid contains vegetable glycerin, propylene glycol and flavorings. Participants with known allergies to these substances will be excluded in the study. The most common reported allergic reaction to these substances is contact dermatitis.

10.2 Nicotine addiction: Participants may be given a study product that contains nicotine, which is an addictive substance. The amount of nicotine they receive from this product depends on what product they are given and how they use it.

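### Criterion 2 admits daily e-cigarette users without requiring nicotine, and the Visit 2 cotinine result decides nothing, so a nicotine-free vaper can be randomized to 18 mg/ml

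*Combined protocol and SAP*

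**What the plan says.** Criterion 2 in section 3.1 gives two routes into the trial. One is smoking at least 5 filtered or machine-rolled cigarettes a day. The other is "or daily e-cigarette use for past year", with nothing on nicotine content or strength.

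At Visit 2 (7.2.3), "A urine sample will also be collected and tested for cotinine using the NICCheck cotinine test". The next step is: "Eligible participants will then be randomized to one of the four conditions". Table 1 in 7.2.5 lists the "NICCHECK Rapid Cotinine Test" as a biomeasure at Visits 2 and 4.

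On the product, 7.4.1 says: "The liquid used in the cartomizer will contain either 0 mg/ml or 18 mg/ml of nicotine". Random assignment alone fixes the concentration. Section 7.4.3 sets a 1:1:1:1 ratio with 56 randomized, stratified by gender and matched for age.

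On risk, 10.2 says: "Participants may be given a study product that contains nicotine, which is an addictive substance". Section 11.5 names one possible direct benefit, which is reduced use of conventional cigarettes.

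**The concern.** The smoking route brings nicotine exposure with it. The e-cigarette route does not, because in this protocol an e-cigarette may hold 0 mg/ml liquid: two of the four study arms do. A cotinine test placed immediately before randomization looks like an eligibility check, but no rule acts on it.

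Two things are at stake.

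- **Participant protection.** A person who currently takes no nicotine could be started on it by randomization. The risk and benefit text is written around people who smoke. Section 10.1 weighs e-cigarette risk against cigarette risk, 10.3 describes withdrawal from smoking less, and 11.5 offers less smoking as the benefit. None of this fits a non-smoking user of nicotine-free liquid.
- **Interpretation of Aim 1.** The rationale in 2.1 attributes cue-reactivity to stimuli becoming linked with the drug's dopaminergic effects. A sample that includes people whose vaping delivers no nicotine is harder to read against that rationale.

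**Working it through.** The plan states no figure on this point, so the check is mainly one of text.

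1. **Inclusion criteria (3.1, nine items).** Only criterion 2 defines product use, and its e-cigarette route names frequency and duration only.
2. **Exclusion criteria (3.2, fourteen items).** None covers nicotine-free use or a negative cotinine result. Pregnancy, tested at the same visit, does have a written consequence (exclusion 4). Cotinine has no counterpart.
3. **Withdrawal before randomization (3.3.1, four items).** None mentions cotinine or nicotine-free vaping. Item 2, "Use of other non-cigarette tobacco products in the past 7 days", is not a nicotine rule. Section 7.2.4 counts the study e-cigarette as a tobacco product ("abstinent from all tobacco products including their ECIG"). On that reading, item 2 could make every vaper a candidate for withdrawal, whatever their liquid contains. That conflicts with criterion 2, and the passages must be reconciled.
4. **Use of the cotinine result (7.2.3, 7.2.5, 7.4.3, 8.3).** No section gives a cut-off, an eligibility consequence, a stratum or an analysis use.
5. **Assignment (7.4.1, 7.4.3).** Nicotine level is set at random, without regard to prior nicotine use or user type.
6. **Aim 1 (1.1, 8.3).** Smokers and e-cigarette users enter without a nicotine condition. The expectations for e-cigarette users are sorted by usual flavor only.

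Together, items 1 to 5 mean that a daily user of nicotine-free liquid who meets the other criteria can be randomized.

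**Chance of a nicotine arm.** Inputs from 7.4.2 and 7.4.3: four arms, two at 18 mg/ml, equal allocation, 56 randomized.

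- Per arm: 56 / 4 = 14. At 18 mg/ml: 2 × 14 = 28. Chance for one participant: 28 / 56 = 0.50.
- Chance that at least one of k such participants is assigned 18 mg/ml: 1 − ∏ (28 − i)/(56 − i), for i = 0 to k − 1.
  - k = 1: 0.500
  - k = 2: 1 − (28 × 27)/(56 × 55) = 1 − 756/3,080 = 0.755
  - k = 3: 1 − (28 × 27 × 26)/(56 × 55 × 54) = 1 − 19,656/166,320 = 0.882

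The calculation for k = 2 and 3 assumes exactly 28 at 18 mg/ml and ignores the gender strata and blocks. The values of k are illustrations, since the documents give no basis for estimating how many such participants would enroll.

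**The case against.** The strongest reply is that this is a gap in wording with little practical effect. Cotinine is tested right before eligible participants are randomized, so an eligibility use may be intended. E-cigarette use history is taken at Visits 1 and 2. The screening instruments described in 7.2.1 and 7.2.2 may record nicotine strength, but their content is not in the documents. Section 3.3.1 lets the investigator remove anyone. In the survey described in 2.2, most e-cigarette users were at 13 to 18 mg/ml, and 15.6 bases recruitment feasibility on smokers. All of this stands as reason to expect few such participants. None of it is a written rule, and discretion applied case by case is less reproducible than a criterion.

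Several stronger readings are tempting, but the documents do not support them.

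- A reader might infer that Aim 1 counts these people as having nicotine-conditioned reactivity. It does not. It tests whether pre-conditioned reactivity exists, and 2.2 allows that other conditioned features of e-cigarette use matter. Nor does current nicotine-free use show that a person never had nicotine pairing: 2.2 describes users who formerly smoked, and criterion 2 does not bar former or lighter current smokers from the e-cigarette route.
- A reader might infer that these people alone spoil the 18 versus 0 mg/ml comparison in Aim 2, because it means continuing or losing nicotine for everyone else. That is wrong for smokers, who may supplement their smoking (3.1, criterion 4) and keep smoking during the study (7.4.4). The mixed meaning of that comparison exists without any nicotine-free vaper.
- A reader might put a figure on lost power. That would need an assumed prevalence, zero reactivity in these participants and a single common effect size. Section 8.3 expects opposite directions for tobacco against strawberry vanilla in different user types, so a single pooled effect is not what is planned for that contrast.
- A reader might want a cotinine condition for smokers too. No defect is shown in the smoking route.

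**Conclusion.** The point holds as a gap in an eligibility rule. Applied exactly, criterion 2 admits daily users of nicotine-free liquid, and the cotinine test that could identify them has no stated consequence. Each such participant has a 50% chance of four weeks at 18 mg/ml, under risk and benefit text that does not fit them. They would also make Aim 1 harder to interpret against its own rationale.

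The per-person chance follows from the allocation ratio alone. How many people are affected is unknown and probably small. Whether unseen screening forms already stop them cannot be determined from the documents. The case for a change therefore rests on participant protection and clarity of the sample, and no power loss is claimed.

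**What to change.** 1. In 3.1, change the e-cigarette route of criterion 2 to daily use of a nicotine-containing e-cigarette for the past year.
2. In 7.2.3, for participants entering by that route, state that the NicCheck result is read before randomization and that a positive result is a condition of randomization. First confirm that the test still detects daily nicotine use after the instructed 14-hour abstinence, and state the cut-off. The documents give neither. A positive result shows nicotine exposure from any source, so it supports the change in criterion 2 and does not replace it.
3. In 3.3.1, add a negative result in these participants to the pre-randomization reasons, so that the replacement rule in 3.3.2 clearly applies. The current list only says that participants will be considered for withdrawal, so the new entry should say that they are not randomized. Reconcile item 2 of that list with criterion 2 in the same edit.

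The cost is wording in three sections and a few extra screen failures. The test is already scheduled before randomization, and 8.1 allows up to 75 enrolled for 56 randomized, a margin of 75 − 56 = 19 for all pre-randomization losses.
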